### **8.2.1.2 Absolute and percentage change from baseline in biochemical measures of disease activity**

For each time window (Month 1, 3, 6, 9, 12, 18, 24, 30, 36), observed values and, the absolute and percentage change from baseline in biochemical measures of disease activity (mean UFC, serum cortisol, serum cortisol after dexamethasone, salivary cortisol, ACTH, fasting serum lipid profile (total cholesterol, HDL, LDL) will be summarized with descriptive statistics. Distribution-free 95% CIs will be given for the median changes.

Furthermore, the time course of these parameters will be displayed graphically using box-plots.

In addition, the absolute and percentage change from the last assessment while on pasireotide s.c. to the last value during the 90-days follow-up period will be summarized in a similar manner.

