3.3 Study population

3.3.1 Patient population

The patient population will consist of male and female patients aged 18 years or older with a diagnosis of Cushing's disease for whom surgery has failed or for whom surgery is not an option and who are treated with pasireotide s.c. Investigators need to ensure that patients enrolled in this study meet the inclusion and exclusion criteria described in [Section 3.3.1.1](#).

Approximately 100 sites in about 35 countries will participate in this study.

The study will enroll a minimum of 100 patients to a maximum of 200 patients. Recruitment is expected to take approximately 96 months. The actual sample size may differ from this planned number.

Inclusion and exclusion criteria

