3.5.2.8 Laboratory evaluations

Mild transient elevations in aminotransferases are observed commonly in patients treated with pasireotide. Rare cases of concurrent elevations in ALT greater than 3xULN and bilirubin greater than 2xULN have also been observed.

Monitoring of liver function is recommended prior to treatment with pasireotide s.c. and after one, two, four, eight and twelve weeks during treatment. Thereafter liver function should be monitored as clinically indicated.

Patients who develop increased transaminase levels should be monitored with a second liver function evaluation to confirm the finding. If the finding is confirmed, the patient should be followed with frequent liver function monitoring until values return to pre-treatment levels. Therapy with pasireotide s.c. should be discontinued in case the patient develops jaundice or other signs suggestive of clinically significant liver dysfunction, in case of a sustained increase in AST or ALT of 5x ULN or greater, or if ALT elevations greater than 3xULN occur concurrently with bilirubin elevations greater than 2xULN. Following discontinuation of treatment with pasireotide s.c. patients should be monitored until resolution.

As the pharmacological activity of pasireotide s.c. mimics that of somatostatin, inhibition of pituitary hormones other than ACTH cannot be ruled out. Monitoring of pituitary function (e.g. TSH/free T₄, GH/IGF-1) before and periodically during pasireotide s.c. therapy should therefore be considered, as clinically appropriate.

Available data on the following laboratory parameters will be collected in this study:

- AST
- ALT
- Alkaline phosphatase
- γ GT
- α -amylase
- Total bilirubin
- WBC
- RBC
- Hemoglobin
- Hematocrit
- Platelets
- Sodium

- Potassium
- Magnesium
- Fasting Plasma Glucose
- HbA1C
- GH
- IGF-1
- TSH
- Free T4
- PT
- APTT

If total bilirubin concentration is increased above 2.0 times upper limit normal (ULN), total bilirubin is recommended to be differentiated into the direct and indirect reacting bilirubin.

All local laboratories contributing to the study should provide the sponsor with a copy of each laboratory's certification and a tabulation of the normal ranges and standard deviations from control values for each of the parameters being evaluated. These laboratory references should be forwarded to the sponsor prior to study start and updated promptly if any information changes during the course of the study.

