6.7 Sample size and power considerations

The sample size for this study is not based on statistical considerations. It is anticipated that up to approximately 100 sites in about 35 countries will participate in the study. The study will enroll a minimum of 100 patients up to a maximum of 200 patients. The actual sample size may differ from this planned number.

7 Procedures and instructions

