### 4.1 Data analysis general information

Data will be summarized and displayed by time intervals based visit windows rather than by a strict visit schedule.

Patients who discontinue treatment prior to the 3-year observation period, will have their safety and efficacy parameters reported according to the time window that corresponds to Day of last dose of pasireotide s.c. plus 90 days.

Continuous variables will be summarized by number of patients, mean, standard deviation, minimum, median and maximum. Categorical variables will be summarized by absolute and relative frequencies. Counts of missing values for both continuous and categorical variables will be reported.

The study is exploratory in nature and no formal hypothesis testing is planned.

Data will be analyzed according to the data analysis Section 6 of the study protocol (as amended on 20SEP2013) which is available in Appendix 16.1.1 of the CSR. Details are given in the following sections and more technical details are provided, as applicable, in Appendix 16.1.9 of the CSR. It is planned that the data from all study sites that participate in this study will be pooled, so that an adequate number of patients will be available for analysis.

Interim analyses will be performed every year as requested by Health Authorities. The first analysis will be conducted about 12 months after the first patient enters the study. After this first analysis there will be one interim analysis on a yearly basis. The recruitment period is expected to be approximately 8 years and each enrolled patient will be followed up for 3 years after enrollment. The final analysis will occur when all patients have completed the study. The same analysis will be performed at all analysis time points.

For each analysis a cut-off date will be set. All data collected up to this cut-off date will be included in the analysis.

Any data collected beyond the cut-off date for an analysis will not be included in the analysis. Only data with an assessment date or event start date (e.g. vital sign assessment date or start date of an adverse event) prior to or on the cut-off date will be included in the analysis. For example, if the cut-off date is 15 June 2010 then an AE starting on 13 June 2010 will be reported, whereas an AE with start date on 17 June 2010 will not be reported.

---

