### 6.2.3 Mixed model for repeated measures

The following SAS code will be used to fit the mixed model for repeated measures.

```
proc mixed;
  class patient window ;
  model outcome = window base /ddfm=kr;
  repeated window /patient = patient type=un;
  lsmeans window / cl;
run;
```

Here, `patient` denotes the patient identifier (e.g. SID1A), `window` the time window assigned, `outcome` the outcome variable (e.g. mean UFC), and `base` the corresponding baseline value.

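### The continuous UFC, cortisol and ACTH analyses pool local-laboratory values without ULN scaling, so absolute changes depend on laboratory mix and a change of laboratory reads as change on treatment

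*SAP*

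**What the plan says.** - **Where values come from.** Protocol 3.3.1: "Approximately 100 sites in about 35 countries will participate in this study". Protocol 3.5.2.8: "All local laboratories contributing to the study should provide the sponsor with a copy of each laboratory's certification and a tabulation of the normal ranges". The same section expects these references to be updated if they change during the study. It is the safety laboratory section, but Protocol 3.5.3.1 leaves UFC to site routine, and neither document names a central laboratory.
- **Pooling.** SAP 4.1: "data from all study sites that participate in this study will be pooled".
- **Continuous summaries.** SAP 8.2.1.2 reports "observed values and, the absolute and percentage change from baseline in biochemical measures of disease activity (mean UFC, serum cortisol", post-dexamethasone cortisol, salivary cortisol, ACTH and lipids, with box-plots and distribution-free intervals for the median changes. There is no version in multiples of ULN.
- **Mixed model.** SAP 6.2.3 fits time window and baseline only. Its inputs are "the outcome variable (e.g. mean UFC), and `base` the corresponding baseline value". It has no laboratory, site or ULN term.
- **Harmonisation.** Protocol 6.5.2.2 and SAP 8.4.2 convert laboratory values to SI units.
- **Where reference ranges are used.** SAP 8.2.1.1 compares mean UFC with the ULN and counts missing ULNs. SAP 8.2.1.3 judges normalisation of the other cortisol measures and ACTH against normal ranges.
- **Comparisons.** SAP 8.2.1 repeats the efficacy analyses by cohort and, except for the symptom-shift endpoint, for German sites.
- **Change of laboratory.** No rule covers a patient whose baseline and later values come from different laboratories.

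**The concern.** SI conversion aligns the unit of measurement. It does not align assays or reference ranges. With 100 to 200 patients over about 100 sites, there are on average one to two patients per site, so a pooled mean combines many laboratories.

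Two patients who both fall from 3 to 1.5 times their own ULN contribute absolute changes that differ by the ratio of those ULNs. A difference in absolute change between cohorts, or between German sites and all patients, could then reflect assays and not response. A patient measured by one laboratory at baseline and another at Month 12 carries the assay difference into the result as if it had occurred on treatment. The plan already uses local ranges for its two binary endpoints, but not for the continuous analyses of the same analytes.

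**Working it through.** The plan has no figure to reproduce: "The sample size for this study is not based on statistical considerations", and no test is planned. The figures below are illustrations under stated assumptions.

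**Inputs**
- True fall in UFC: 47%, the approximate median decrease in the earlier phase III study (Protocol section 1).
- Baseline: 100 in the units of laboratory A (assumed).
- Laboratory B reads k times laboratory A, and its ULN is also k times larger. The documents give no value for k; 1.2, 1.5 and 2.0 are assumed.
- s = share of patients measured by laboratory B.

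**1. Laboratory mix, no switching**

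Mean absolute change = -47 × [(1 - s) + s × k]. For k = 1.5 and s = 0.8 this is -47 × 1.4 = -65.8.

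| k | s = 20% | s = 50% | s = 80% |
|---|---|---|---|
| 1.2 | -48.9 | -51.7 | -54.5 |
| 1.5 | -51.7 | -58.8 | -65.8 |
| 2.0 | -56.4 | -70.5 | -84.6 |

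Two groups with the same true response but 20% and 80% of patients in laboratory B differ in mean absolute change by a ratio of 1.16/1.04 = 1.12, 1.40/1.10 = 1.27 or 1.80/1.20 = 1.50. Percentage change is -47% in every cell. In multiples of ULN the change is also the same in every cell.

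**2. A patient who changes laboratory**

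With no true change, A to B gives k - 1 and B to A gives 1/k - 1. With the true fall, these become 0.53k - 1 and 0.53/k - 1.

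| k | A to B, no change | B to A, no change | A to B, true -47% | B to A, true -47% |
|---|---|---|---|---|
| 1.2 | +20% | -16.7% | -36.4% | -55.8% |
| 1.5 | +50% | -33.3% | -20.5% | -64.7% |
| 2.0 | +100% | -50% | +6.0% | -73.5% |

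If 10% of laboratory-A patients move to B, the mean absolute change shifts by 0.10 × 53 × (k - 1) = 1.06, 2.65 or 5.3. Divided by 47, that is 2.3%, 5.6% or 11.3% of the true fall.

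**3. Uneven dropout**

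Simulation: 150 patients, half in each laboratory, 100 runs, two post-baseline windows with no true change between them. Retention at window 2 is 30% in A and 80% in B. The model has window and baseline, fitted by GEE with exchangeable correlation as a stand-in for the SAP's PROC MIXED code.

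| k | Model mean, window 1 | Model mean, window 2 | Crude mean, window 2 |
|---|---|---|---|
| 1.0 | 199.7 | 198.2 | 198.5 |
| 1.2 | 220.4 | 219.8 | 228.8 |
| 1.5 | 248.8 | 248.4 | 271.4 |
| 2.0 | 298.0 | 301.1 | 348.7 |

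The level of the model means follows the enrolled mix. The contrast between windows stays near zero, because baseline is a covariate. The crude window-2 mean drifts. For k = 1.5 the share of B among those still observed is 0.8/(0.8 + 0.3) = 73%, so the expected multiplier goes from 1.25 to 1.36, a 9% rise with no biological change. After scaling to ULN, the model means are about 198 to 201 for every k.

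**The case against.** The case for leaving the plan alone has weight. The study is a single-arm safety study, and "The study is exploratory in nature and no formal hypothesis testing is planned". These are secondary descriptive summaries. The first-listed efficacy endpoint already uses the ULN, and normalisation uses local ranges. Percentage change is reported beside absolute change, and a proportional assay difference cancels in it while the patient stays with one laboratory. Protocol 6.5.1.2 also permits log-transformed analysis. All of this stands and limits the point. The log option, however, is not carried into the SAP's model code, and it would not correct a change of laboratory.

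A reader might also infer more than the documents support:
- **That values are pooled in unconverted local units.** SI conversion is planned. It is stated in the safety sections, so only its application to the efficacy analytes needs confirming.
- **That dropout creates a false time trend in the mixed model.** In the check above the baseline covariate largely removes it. The drift is in crude window means.
- **That confidence intervals widen by a known amount, as if part of the sample were lost.** SAP 8.2.1.2 plans distribution-free intervals for medians, to which an inflation of the standard deviation does not carry over directly. No ULN spread is given either.
- **That a pre-entry UFC used as baseline came from another laboratory.** Protocol 3.5.3.1 does not say so.
- **That multiples of ULN should replace the planned scale.** Absolute and percentage changes are the endpoints defined in Protocol 2.2.1.

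**Conclusion.** The concern holds within limits. Observed values, absolute changes, crude window means and the level of the mixed-model means depend on laboratory mix, and so do comparisons of these quantities between cohorts or with the German-site subgroup. A change of laboratory contaminates both absolute and percentage change. Percentage change in patients who stay in one laboratory, the model's window-to-window contrasts and the two range-based endpoints are largely unaffected.

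The size cannot be stated from the documents. The illustrated effect of a switch, +20% to +100% or -17% to -50%, rests on an assumed assay ratio of 1.2 to 2.0, and the frequency of switching is unknown. The protection of percentage change rests on assay differences being proportional. The protection of the model contrasts rests on a simulation with a stand-in for the planned model. The matter affects how secondary efficacy results are read. It does not touch the primary safety objective.

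**What to change.** 1. In SAP 8.2.1.2 and 6.2.3, add change-from-baseline summaries, box-plots and a mixed model in multiples of the measuring laboratory's ULN. Do this for mean UFC (each 24-hour value divided by its own ULN before averaging), and for serum cortisol, salivary cortisol, ACTH and post-dexamethasone cortisol where the reference range supports it. Keep the protocol-defined SI-unit absolute and percentage changes beside them.
2. Where the laboratory or its reference range can be identified, report for each window how many patients have a different one from baseline, and repeat the analysis without them.
3. State that SI conversion applies to the efficacy analytes.

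**Cost.** SAP wording, one derived variable per analyte and an extra set of outputs. ULN and normal ranges are already needed for SAP 8.2.1.1 and 8.2.1.3. The documents do not show that a laboratory identifier is held for each sample, so the second step may have to rely on a change in reference range. Values with a missing ULN drop out of the scaled analysis. Scaling also helps only as far as each ULN tracks its assay's calibration.

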3.1.1 Safety and tolerability assessments

All safety assessments will be collected from patient's enrollment into the study by signing the informed consent or acknowledging an equivalent document (e.g., written information) as per country regulation until the last dose of pasireotide s.c. at the patient's last follow-up visit within the 3 year observation period or until 3 months after the last dose for patients who permanently discontinue pasireotide s.c. prior to completing 3-year observation period.

- Adverse events and Serious Adverse Events will be followed-up and collected from patient's enrollment into the study until 28 days after the last dose of pasireotide s.c. at the patient's last follow-up visit. Adverse events and Serious Adverse Events will be collected until 3 months after the last dose for patients who permanently discontinue pasireotide s.c. prior to completing 3-year observation period.
- Special safety assessments will be collected from patient's enrollment into the study until the last follow-up visit as available or until 3 months after the last dose for all available safety parameters, for patients who permanently discontinue pasireotide s.c. prior to completing the 3-year observation period. Safety data to be collected include: vital signs, blood pressure, heart rate, body temperature, blood glucose (fasting plasma glucose, HemoglobinA1c), hormones (IGF-1, GH, TSH/free T₄), liver enzymes (AST, ALT, alkaline phosphatase, γGT, total bilirubin), hematology, electrolytes, immunological events (e.g., allergic reactions: rash, pruritus, injection site reactions), gallbladder ultrasound and ECGs.
- Medical history including history of smoking, history of alcohol use, presence of hepatitis B and C infection will be recorded at patient's entry in the study. Prior/concomitant medications/significant non-drug therapies (e.g., surgery, radiation) will be collected from patient's enrollment into this study until the last follow-up visit as available or until 3 months after the last dose for patients who permanently discontinue pasireotide s.c. prior to completing the 3-year observation period.

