3.4.1.1 Treatment discontinuation

Patients who permanently discontinue treatment with pasireotide s.c. prior to the 3-year observation period will have to be withdrawn from this study. Patients who discontinue pasireotide s.c. treatment because of an adverse event, must be followed by the investigator until resolution of the AE or until 3 months following discontinuation of drug whichever is longer.

All available safety and efficacy parameters will be collected for a period of 3 months following the last dose of pasireotide s.c. for patients who permanently discontinue pasireotide s.c. prior to completing the 3-year observation period.

Patients may voluntarily withdraw from this study or discontinued at the discretion of the investigator at any time. If such withdrawal occurs the investigator should determine the primary reason for a patient's premature withdrawal from this study. The withdrawal reason should be categorized into one of the following:

- Adverse event(s)
- Protocol deviation
- Subject withdrew consent or equivalent document (e.g., written information) as per country regulation
- Lost to follow-up
- Administrative problems
- Death
- Unsatisfactory therapeutic effect

For patients who are lost to follow-up, the investigator should show "due diligence", for the first 3 months after the last known date the patient took pasireotide, by documenting in the source documents steps taken to contact the patient, e.g. evidence of two certified letters, dates of telephone calls, sent emails.

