The data will be summarized with respect to demographic and baseline characteristics, safety observations and measurements as well as efficacy assessments. Data will be summarized and displayed by time intervals based visit windows rather than by a strict visit schedule, in order to reflect the nature of this study. Details on definition of time windows will be provided in the Report and Analysis Plan (RAP). Furthermore, for patients who discontinue treatment prior to the 3-year observation period, their safety and efficacy parameters will be reported according to the time window that corresponds to 90 days from the Day of last dose of pasireotide s.c. Continuous variables will be summarized by number of patients, mean, standard deviation, minimum, median and maximum. Categorical variables will be summarized by absolute and relative frequencies. Counts of missing values for both continuous and categorical variables will be reported. Results with and without imputation will be reported.

Baseline assessment refers to the last assessment prior to the patient's first pasireotide s.c. dose recorded after the signing of the informed consent or acknowledging an equivalent document (e.g., written information) as per country regulation. For some assessment this definition maybe expanded to include the first assessment post the first pasireotide s.c. dose recorded after informed consent or an equivalent document (e.g., written information) as per country regulation.

In this study, the first analysis will occur at about 12 months after the first patient enters the study. After this first analysis there will be one analysis on a yearly basis. The final analysis will occur when all patients complete the study. The same analysis will be performed for all analyses time points.

Assessment time points are considered relative to first pasireotide s.c. dose recorded on or after the singing of the informed consent or acknowledging of an equivalent document (e.g., written information) as per country regulation, unless noted otherwise.

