6.5.1.2 Absolute and percentage change from baseline secondary efficacy endpoints

For each visit window, the absolute and percentage change from baseline values will be summarized by number of patients, mean, standard deviation, median, minimum, maximum. Furthermore, depending on the distribution of the data, the central tendency of the data will be summarized by generating a 95% CI for the mean absolute change and mean percentage change from baseline values, for approximately normally distributed data. In contrast, for heavily skewed data the 95% CI for the median might be generated, or the mean of the log transformed data might be analyzed as described for approximately normally distributed data.

6.5.1.3 Absolute change between the last assessment on drug and 3 months later for continuous secondary efficacy endpoints

For each efficacy assessment (see [Section 6.5.1](#) for the list of assessments), if sufficient patients have assessments 3-months after permanent pasireotide s.c. discontinuation, the absolute change from the last assessment while on pasireotide s.c. to three months after drug discontinuation, will be similarly summarized.

6.5.1.4 Normalization of biochemical measures of disease activity and clinical symptoms of Cushing's disease

For each appropriately defined visit window, the number and percentage of patients with normalization of biochemical measures of disease activity will be presented together with corresponding exact 95% confidence interval (CI).

For each variable associated with clinical symptoms of Cushing's disease, and for each appropriately defined visit window, the number and percentage of patients with favorable shift from baseline will be presented together with corresponding exact 95% CI. Furthermore, shift tables from baseline to certain visit windows might be presented.

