**Table 6-2 Time windows**

Window name (1)	Window No.	Target Day	Starting Day of Window	Ending Day of Window
Baseline	1	-	-	1 (2)
Month 1	2	30	2	60
Month 3	3	91	61	136
Month 6	4	183	137	229
Month 9	5	275	230	320
Month 12	6	365	321	458
Month 18	7	550	459	641
Month 24	8	731	642	821
Month 30	9	914	822	1005
Month 36	10	1096	1006	1187
After Month 36	11	-	1188	No upper limit
Last value on treatment		DLD (3)	2	DLD + gap (4)
Day 90 after last dose		DLD + 90 days	DLD+gap+1 days	DLD + 90 days

(1) Windows are named according to their target days. For example, the target day for window Month 6 is  $6 * 30.4375$  days, where 30.4375 is the standard length of a month ( $=365.25/12$ ). The starting day of the window is the midpoint between target day of previous window and current window and the ending day is the midpoint between target day of current window and next window.  
 Note that only post-baseline on-treatment assessments are assigned to windows Month 1, Month 2, etc., up to 'after Month 36'.

(2) For some parameters, the earliest assessment after first dose is used as baseline assessment if no assessment is available before or on the day of first dose. This assessment is then exclusively used as baseline assessment although it falls into a post-baseline window.

(3) DLD = Day of last dose of pasireotide s.c.

(4) gap = number of days after DLD during which assessments and events are considered on-treatment. gap=3 for efficacy analyses, gap=28 for safety analyses

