#### 8.2.1 Secondary efficacy endpoints

The secondary efficacy endpoints are as follows:

---

1. Proportion of patients with a mean UFC  $\leq$  ULN at 1, 3, 6, 12, 24 and 36 months after enrollment into the study.
2. The absolute and percentage change from baseline in biochemical measures of disease activity (mean UFC, serum cortisol, serum cortisol after dexamethasone, salivary cortisol, ACTH, fasting serum lipid profile (total cholesterol, HDL, LDL)) over time.
3. Proportion of patients achieving normalization of biochemical measures of disease activity (serum cortisol, serum cortisol after dexamethasone, salivary cortisol, ACTH) over time, where normalization refers to being within the upper and lower limit of normal ranges.
4. The absolute and percentage change from baseline in clinical signs and symptoms (blood pressure, body weight, body mass index, waist circumference) over time.
5. The proportion of patients with favorable shift from baseline in clinical symptoms of Cushing's disease over time.
6. The change from the last dose of pasireotide s.c. to 90 days after permanent discontinuation of pasireotide s.c. for patients who discontinue pasireotide s.c. prior to completing 3-year observation period. This change will be evaluated for all available continuous efficacy parameters.
7. The absolute and percentage change from baseline in tumor size over time.
8. The absolute and percentage change from baseline in patient reported outcome questionnaires (Cushing QoL and EURO QoL) over time.

All efficacy analyses will be done for all patients in the FAS and for the two cohorts. And all efficacy analyses except those under 5 will be done for the subgroup patients from German sites. Additionally, the efficacy analyses described under 1, 2, and 3 above will be repeated for the following subgroups of patients:

- Patients treated with monotherapy pasireotide s.c. throughout the study
- Patients treated with a combination of pasireotide s.c. with any other therapy for Cushing's disease throughout the study
- Patients who switched from monotherapy to combination therapy or vice versa at any time during the study

For all continuous efficacy variables (biochemical measures of disease activity, blood pressure, body weight, body mass index, waist circumference, tumor size), a Mixed Effects Repeated Measures Model will also be employed to assess the longitudinal changes in these variables.

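### The post-discontinuation change labelled 'Day 90' accepts a lone value from a few days after stopping, excludes most visits made at exactly 3 calendar months, and does not separate patients who start another Cushing's therapy

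*SAP*

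**What the plan says.** The change after stopping is a stated secondary objective and endpoint (Protocol 2.2 and 2.2.1). The documents describe its end point in two ways.

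- **Three months.** Protocol 6.5.1.3 plans, "if sufficient patients have assessments 3-months after permanent pasireotide s.c. discontinuation", to summarise "the absolute change from the last assessment while on pasireotide s.c. to three months after drug discontinuation". Protocol 3.4.1.1 sets the collection period: "All available safety and efficacy parameters will be collected for a period of 3 months following the last dose of pasireotide s.c".
- **Ninety days.** The opening of Protocol Section 6 reports early stoppers "according to the time window that corresponds to 90 days from the Day of last dose of pasireotide s.c". SAP 8.2.1, item 6, follows this: "The change from the last dose of pasireotide s.c. to 90 days after permanent discontinuation of pasireotide s.c".

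For biochemical measures, SAP 8.2.1.2 takes "the absolute and percentage change from the last assessment while on pasireotide s.c. to the last value during the 90-days follow-up period". SAP 8.2.1.1, 8.2.1.4 and 8.2.1.6 use the same last-value rule for mean UFC status, clinical signs and tumour volume.

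In SAP Tables 6-2 and 6-3 the row 'Day 90 after last dose' has its target at day of last dose (DLD) + 90. It runs from DLD + gap + 1 to DLD + 90, where "gap=3 for efficacy analyses, gap=28 for safety analyses".

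On other treatment, Protocol 3.1.1 collects concomitant drugs and significant non-drug therapies, with surgery and radiation as examples, "until the last follow-up visit as available or until 3 months after the last dose for patients who permanently discontinue". No section of either document uses these data to flag, split or censor the post-discontinuation change.

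**The concern.** Two features make the table hard to read as a 3-month off-drug change.

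**Timing.** The window is wide before its target and closed after it. With no imposed visit schedule, patients contribute whatever last value they have, so one patient's result may be a few days off drug and another's nearly three months. Values collected just after day 90, within the protocol's 3-month period, are dropped.

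**Other therapy.** Unsatisfactory therapeutic effect is a listed withdrawal reason (Protocol 3.4.1.1), and the protocol's introduction describes severe morbidity, so some patients can be expected to start another treatment soon after stopping. The last value in the window is the one most likely to follow that start. A reader of the pooled table cannot tell how far it reflects withdrawal and how far replacement therapy.

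What is at stake is the interpretation of a descriptive secondary endpoint. No hypothesis test or error rate is involved.

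**Working it through.** **1. The plan's own Month 3 window, reproduced.** Inputs are the standard month of 365.25/12 = 30.4375 days and the midpoint rule in the Table 6-2 footnote.

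- Target: 3 × 30.4375 = 91.3, giving 91.
- Start: (30.4375 + 91.3125)/2 = 60.9, giving 61.
- End: (91.3125 + 182.625)/2 = 136.97, giving 136.

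These match the table. The ordinary window allows 136 − 91 = 45 days after its target.

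**2. The post-dose window.**

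| | Start | End | Eligible days | Days allowed after target |
|---|---|---|---|---|
| Efficacy (gap 3) | DLD + 4 | DLD + 90 | 90 − 4 + 1 = 87 | 0 |
| Safety (gap 28) | DLD + 29 | DLD + 90 | 90 − 29 + 1 = 62 | 0 |

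Elapsed time can differ between patients by up to 86 days for efficacy and 61 days for safety. Because the target is the window's last day, the closest-to-target rule in SAP 6.1.7 and the last-value rule choose the same value. An early value is used only when nothing later exists.

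**3. Visits at exactly 3 calendar months.** Counting every last-dose date in a four-year cycle (1,461 dates) gives:

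| Days in 3 calendar months | Dates |
|---|---|
| 89 | 87 |
| 90 | 216 |
| 91 | 313 |
| 92 | 845 |

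The share after DLD + 90 is (313 + 845)/1,461 = 1,158/1,461 = 79%. In a year with no leap-day effect, the dates from 1 March to 29 November qualify: 274/365 = 75%. A 13-week visit (91 days) is excluded and a 12-week visit (84 days) is kept.

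**4. What a DLD + 92 limit recovers.** Three calendar months never exceed 92 days, so every exact 3-month visit is kept. If visits instead scatter evenly by ± w days around the exact date (an assumption; the documents give no distribution), days 91 and 92 hold 2/(2w + 1) of them for w of 3 or more:

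| Scatter | Excluded by DLD + 90 | Recovered by DLD + 92 | Still excluded |
|---|---|---|---|
| none | 79% | 79% | 0% |
| ± 3 days | 62% | 2/7 = 29% | 33% |
| ± 7 days | 55% | 2/15 = 13% | 42% |
| ± 14 days | 53% | 2/29 = 7% | 46% |

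Visits still excluded fall after day 92, beyond the planned collection period.

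**5. Whether existing subgroups separate new therapy.** SAP 8.2.1 repeats analyses 1, 2 and 3 by monotherapy, combination and switch. Item 6 is not in that list, and combination means therapy given with pasireotide. The exposure summaries in SAP 8.3 include only patients still receiving pasireotide at the end of each period. Neither identifies therapy started after the last dose.

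**6. Size of the mixing.** The documents give neither the share of stoppers who start a new therapy (s) nor the fraction of any rebound it removes (e). If the observed change is (1 − s × e) of the untreated change, then s = 0.1 and e = 0.25 give 0.975, while s = 0.7 and e = 1 give 0.30. These inputs are assumptions, and the formula itself presumes the direction. The range shows only that the documents leave the size open.

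**The case against.** The strongest reply has four parts.

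- **The SAP follows the protocol.** Protocol Section 6 does name 90 days. That explains the upper limit. It does not explain a lower limit of DLD + 4 for a result labelled 'Day 90', nor the mismatch with the protocol's own 3-month collection and end point.
- **The rule takes the last value, not any value.** This is correct, and it limits the problem to patients with no later value. Nothing requires a later value, so such patients can occur. The DLD + 4 start applies to efficacy only.
- **Calendar dates are not visits.** This is also correct. A reader might infer from the 75–79% that most 3-month assessments will be lost. The documents do not support that: visit days are unknown, the overshoot is one or two days, and a patient with an earlier value in the window still contributes.
- **A change regardless of later therapy is a legitimate target.** The objective is to document changes in a real-life, exploratory study, and neither document claims to estimate a pure withdrawal effect. This stands, and it is why the all-patients summary should stay. Replacing it with pre-therapy values alone could add selection bias if patients who relapse faster are treated sooner.

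**Conclusion.** The point holds on both parts, as a matter of interpretation for a descriptive secondary endpoint.

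The window part rests on the SAP's stated bounds and on calendar arithmetic. A lone early efficacy value can stand as the 90-day result, and an exact 3-month visit falls outside for 75% to 79% of last-dose dates. How many patients are affected is unknown.

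The therapy part is an omission: patients with and without a new Cushing's therapy after the last dose are pooled, although the data to tell them apart are planned. A reader might infer that the analysis understates loss of control. The documents do not support that. They give no rate or effect of new therapy, and patients who stop for unsatisfactory effect may have little response to lose. Neither the size nor the direction can be derived.

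A reader might also infer that the window should run as far past its target as the Month 3 row does. That would reach well beyond the planned 3-month collection.

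**What to change.** 1. **Window.** In SAP Tables 6-2 and 6-3, extend the upper bound of the 'Day 90 after last dose' row to at least DLD + 92, so that it matches the 3-month collection period. Either set a later lower bound for the value carrying that label, or report elapsed days since last dose and show early values in a separate row. Align the 90-day wording in SAP 4.1 and 8.2.1 to 8.2.1.6, and record the change in SAP Section 3, which now reads as not applicable.
2. **Split.** Keep the planned all-patients summary. Add a descriptive split by whether a new Cushing's therapy (drug, surgery or radiation) started between the last dose and the assessment, using the therapy data collected under Protocol 3.1.1.
3. **Optional support.** A summary limited to values before any new therapy may be added, with elapsed days shown and the selection caveat stated. It should not be restricted to late values, because patients treated early may have only early values from before that therapy.

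The cost is SAP wording, one derived flag and extra rows in existing tables; no new data are needed. The downside is smaller groups per row in a study of 100 to 200 patients, of whom only early stoppers contribute. A later lower bound also moves patients with only early values out of the main row.
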